1.2 Primary Study Endpoints

- Change in Overall SPADI scores at baseline compared to 2,4, and 6 months.
- Adverse reactions to the steroid

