7.0 Study Design and Procedures

7.1 Study Design

This is a prospective, randomized, three-arm, double-blind clinical trial comparing steroid concentrations in patients undergoing intraarticular glenohumeral joint injections.

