7.2.2 Clinic appointment

A member of the research team will meet with the patient. The consent will be read and reviewed with the patient. After obtaining informed consent, the patient will be asked to complete the SPADI. This will be completed on paper and entered in to the REDCap database by a member of the research team. Patients will be asked questions regarding nicotine use, pain relievers use 24 hours prior to the injection, recent therapies for shoulder pain, and dominant arm. This data will be recorded in the research records. The coordinator will randomize the patient. The patient will be randomized into one of three study arms 1) 20 mg Triamcinolone with 3 cc of 1% Lidocaine, 2) 40 mg Triamcinolone with 3cc of 1% Lidocaine, or 3) 80mg Triamcinolone with 3cc of 1% Lidocaine. The injection will be prepared by a non-blinded investigator based on the study arm selected following standard of care protocols. Standard clinic protocol involves applying a patient label to the syringe. To assist with the blinding process, an additional label will be applied to the body of the syringe to ensure the volume of the syringe cannot be determined.

For the actual injection we will be using patients from 3 physicians who are investigators for this study. The same 3 physicians will administer the injection to their individual patients. Each of these investigators have performed a minimum of 800 injections and will be using the exact same methodology for providing the Ultrasound Guided injection. Since the injections will be performed under guidance and the approach of the injection will be identical we anticipate minimal operator effect on our study results.

An ultrasound unit will be used to identify the Glenohumeral joint with the patient in a lateral recumbent position. A posterior approach will be utilized to access the Glenohumeral space. The joint will be scanned and a marking pen will be used to mark the area of approach. The skin and probe will then be sterilized. The probe will then be replaced on the previously marked position and a 22 gauge spinal needle will be used to direct the injection into the glenohumeral space. The needle will be visualized throughout the procedure. Images will be taken of the joint before the injection, while the needle is in the joint, and post injection. They will be saved and uploaded into the medical record. Pre and post pain levels will be elicited from patient. The patient will be blinded to the study arm selected.

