7.2.3 Post-Clinic appointment

Patients will be contacted via telephone at 2 weeks to determine if any significant adverse outcomes have occurred. Patients will be contacted at 2 months, 4 months, and 6 months following the injection by email and/or phone call for completion of the SPADI and assessment of any adverse events that may have occurred as a result of the injection. Patients will also be asked what, if any, pain medications have been used in the month prior to the phone call. Patients will be given the option to complete the SPADI using the REDCap system or on paper. Patients wishing to complete the survey online will be emailed a link to access REDCap. A paper version of the survey will be mailed to the patient if that is their preferred method. A self-addressed stamped envelope will be included with the mailings. If the patient perceives that they have experienced an adverse effect the research coordinator will make a detailed record of the patient experience and the PI of the study will be contacted. .

At 12 months following the initial injection, in addition to a chart review, the patient will be contacted to determine the outcome of their shoulder pain and determine if the patient underwent any additional procedures and/or surgeries to the shoulder.

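### The role that randomises the patient also records adverse effects, a primary endpoint, and the plan does not keep the allocated arm from that role

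*Combined protocol and SAP*

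**What the plan says.** Section 7.1 describes a "prospective, randomized, three-arm, double-blind clinical trial". Section 1.2 lists two primary endpoints, the change in SPADI and "Adverse reactions to the steroid".

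On allocation, section 7.2.2 says "The coordinator will randomize the patient". It continues: "The injection will be prepared by a non-blinded investigator based on the study arm selected". An extra label on the syringe body hides the volume. The section closes its account of blinding with "The patient will be blinded to the study arm selected".

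On adverse effects, section 7.2.3 has patients telephoned at 2 weeks and contacted by email or phone at 2, 4 and 6 months. If a patient perceives an adverse effect, "the research coordinator will make a detailed record of the patient experience and the PI of the study will be contacted". Under section 10.1 the research coordinator fills in the report forms and logs and, with the principal investigator, confirms the adverse-event log. One physician makes all the assessments. Section 10.3 names two sources of safety information, the follow-up phone interviews and the electronic medical record.

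**The concern.** One role stands at both ends of the comparison: it carries out the allocation, and it writes the account from which a primary endpoint is built. If that role knows the arm, the fullness of the record can depend on the dose.

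This matters more for adverse reactions than for most endpoints. The hypothesis in section 1.1 is that the low dose works as well as the others with fewer side effects, so a dose-related difference in side effects is what the team expects to find. A recorder who knows that a patient had the highest dose may take a fuller account of a vague complaint than one who knows that the patient had the lowest. That would create or enlarge the expected difference. Analysis cannot repair this afterwards. Fisher's exact test, which section 8.3 gives for categorical variables, takes the recorded counts as they stand.

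**Working it through.** No arithmetic applies, because no sample size, power or significance level enters the point. The check is to follow the allocation and the adverse-event record through the protocol and ask, for each role, whether it is said to be blinded.

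| Role | Task | What the protocol says about blinding |
|---|---|---|
| Patient | Reports adverse effects | Blinded, expressly (7.2.2) |
| Preparer of the syringe | Draws up the allocated dose | Not blinded, expressly (7.2.2) |
| Injecting physician | Gives the injection | Not stated; the volume-hiding label implies masking (7.2.2) |
| Coordinator | Randomises (7.2.2); records adverse effects (7.2.3); completes forms and logs and helps confirm the log (10.1) | Not stated |
| Follow-up caller | Asks about adverse events (7.2.3, 10.3) | Not stated; the caller's role is not named |
| Physician assessor | Assesses all adverse events (10.1) | Not stated |

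1. *Is it one coordinator?* Section 7.2.2 says the coordinator; sections 7.2.1, 7.2.3 and 10.1 say the research coordinator. No other coordinator is named, so the natural reading is a single role.

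2. *Does the coordinator see the arm?* The protocol does not say. The coordinator randomises, and the preparer then acts on the arm selected. How the sequence is generated, how it is concealed and how the result reaches the preparer are not described. The arm could pass through the coordinator, or a system could release it to the preparer alone. The text allows both.

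3. *Does the syringe label help?* It protects whoever handles the filled syringe without having prepared it. It does nothing about knowledge gained at randomisation.

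4. *What stands between the coordinator's record and the endpoint?* A blinded patient must first perceive an effect. The principal investigator is then contacted and shares in confirming the log, a physician assesses the event, and the medical record is a second source. The assessor's blinding is not stated, however, and the assessor may rely on the account that the coordinator wrote. Section 7.2.3 describes no structured checklist that would limit the recorder's discretion.

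The role overlap is therefore explicit. The coordinator's knowledge of the arm is possible under the text and is not excluded by it.

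**The case against.** The strongest reply is that unblinding of the coordinator is nowhere stated. The trial is declared double-blind, and section 7.2.2 singles out one role as non-blinded, which suggests that the others are meant to be blinded. To randomise a patient is not necessarily to see the result. This stands as far as it goes: a reader might infer that the coordinator certainly knows the arm, and the documents do not support that. They do not exclude it either, and in a double-blind trial the plan should.

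The second reply is that the coordinator does not determine the endpoint alone. The safeguards in step 4 are real, and they make the exposure smaller than the role overlap alone suggests. Nor is the coordinator named as the person who makes the follow-up calls; section 7.2.3 uses the passive and section 10.3 names no caller. Biased questioning by the coordinator is therefore a further inference, whereas biased recording follows from a task that the plan does assign. What remains is that an event thinly recorded may be judged on that thin record.

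A reader might also infer that the SPADI is exposed in the same way, because section 7.2.3 mentions phone contact for its completion. The same paragraph then offers completion in REDCap or on paper, with an emailed link or a mailed form. Read together, the phone is a means of contact and the patient fills in the form. The point is confined to adverse reactions.

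**Conclusion.** The point holds for the adverse-reaction endpoint. The plan gives allocation and adverse-event recording to one role, and it does not say that this role, the follow-up caller or the physician assessor is blinded. That is more than a missing detail, because the overlap is written into the plan.

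The size of any bias cannot be derived. The documents give no expected rate of adverse reactions and nothing on how recording would change with knowledge of the arm, so any percentage would be invented. The direction of concern is towards the difference that the protocol expects.

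The conclusion rests on two assumptions: that the coordinator in 7.2.2 is the research coordinator of 7.2.3 and 10.1, and that no concealed allocation system exists outside the text. If such a system is in use, the remedy reduces to describing it and stating who is blinded.

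**What to change.** In section 7.2.2, state that the allocated arm is shown only to the non-blinded investigator who prepares the syringe. Either of two arrangements would do this:

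- the preparer runs the randomisation; or
- the coordinator triggers it in a system that releases the arm to the preparer alone, which leaves the present roles as they are.

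Then add two statements, with matching wording in 7.2.3 and 10.1:

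- the preparer does not elicit, record or assess adverse events;
- the coordinator, the follow-up callers, the injecting physician and the adverse-event assessor stay blinded until database lock.

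The cost is a few sentences and an access setting in whichever system issues the allocation. The preparer must be available at each randomisation, which is a small burden because that person already prepares each syringe. The documents do not say who the preparer is or what else that person does. The sponsor should check that the role can be kept apart from follow-up; if it cannot, someone else must take over the adverse-event tasks.

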8.2 Sample size determination

This is a three arm trial comparing three different doses of steroid (20mg, 40mg, 80mg) in patients with glenohumeral arthritis. The primary endpoint is change in overall pain score on the SPADI at two, four, and six months from baseline. The sample size is determined based on assuming a minimal clinically meaningful difference in the 20mg vs 80mg groups as well as conducting non-inferiority tests in the 20mg vs 40mg and 40mg vs 80mg groups. Let d_1 , d_2 , and d_3 be the average change in overall pain scale for the three different doses (low, medium, high). For the first part, in the 20mg vs 80mg groups, we wish to have sufficient statistical power based on the assumption of a moderate Cohen effect size of .5 (e.g. differences of 40 vs 20 with a standard deviation of 40). This requires a sample size 51 per group based on a two-sided 80%-power 5%-level t-test. For the non-inferiority test, we assume d_1 , d_2 , and d_3 are 40, 36, and 32 (so $d_3-d_2=d_2-d_1=4$) with a standard deviation of 20. Allowing for a non-inferiority margin of 15 (so that differences less than 15 are deemed clinically non-inferior), a sample size of 52 per group based on an 80%-power 2.5%-level (since there are two tests) non-inferiority test (<http://powerandsamplesize.com/Calculators/Compare-2-Means/2-Sample-Non-Inferiority-or-Superiority>). Allowing for 10% loss to follow-up yields a final sample size calculation of **57 per group for each of the three groups**.

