8.3 Statistical methods

The primary endpoint is change from baseline of the shoulder pain and disability index (SPADI). The low dose and high dose changes will be analyzed with a two-sided two-sample t-test. Noninferiority tests with a margin of .5 will be used to test for a clinically meaningful difference between 20mg and 40mg doses and the 40mg and 80mg doses. The three groups will be summarized with descriptive statistics and univariate statistical tests using analysis of variance for normally distributed continuous variables, Kruskal-Wallis test for non-normally distributed continuous variables, and the Fisher's exact test for categorical variables. The demographic data and SPADI data will be analyzed accordingly. All statistical analyses, graphics, and reports will be prepared following best practices in conducting reproducible research in statistics utilizing various software packages built around the R software platform. [name]., Associate Professor, will serve as the Biostatistician for this study.

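### Physician is neither a stated randomisation stratum nor a term in the analysis; stratifying and adjusting for it would cheaply remove chance imbalance and some noise, though the comparison is not biased as planned

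*Combined protocol and SAP*

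**What the plan says.** Section 7.2.2 takes patients from three physician investigators: "The same 3 physicians will administer the injection to their individual patients". A patient's injector is therefore settled by clinic scheduling and not by the trial.

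The same section gives two reasons for not expecting operators to matter. One is experience and common method: "Each of these investigators have performed a minimum of 800 injections and will be using the exact same methodology". The other is ultrasound guidance with a common approach: "Since the injections will be performed under guidance and the approach of the injection will be identical we anticipate minimal operator effect on our study".

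Allocation is described in 7.2.2 only as "The coordinator will randomize the patient", into one of three arms. No blocking, stratification or minimisation is mentioned.

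Section 8.3 plans, for 20 mg against 80 mg, "The low dose and high dose changes will be analyzed with a two-sided two-sample t-test". For adjacent doses it plans "Noninferiority tests with a margin of .5 will be used to test for a clinically meaningful difference between 20mg and 40mg doses", and likewise for 40 mg against 80 mg. Beyond that, "The three groups will be summarized with descriptive statistics and univariate statistical tests using analysis of variance for normally distributed continuous variables", with rank-based and exact tests for other kinds of variable. No planned test contains a physician term.

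**The concern.** The reasons in 7.2.2 bear on how the needle is placed. They do not say whether the three physicians' patients resemble one another in severity, expectations or likely response, and no other section compares the caseloads. The expectation of minimal operator effect therefore leaves open the component of between-physician variation that comes from the patients.

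Two things follow. First, the mix of physicians can differ by chance between dose arms; nothing stated in the plan prevents this, and nothing in the analysis adjusts for it. Second, any variation between physicians stays in the error term of the t-test and the non-inferiority tests, where one factor could remove it. What is at stake is precision, and how easily an arm difference can be read when the arms differ in physician mix.

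**Working it through.** **Inputs from section 8.2.** Non-inferiority SD 20, assumed adjacent-dose difference 4, margin 15, 2.5% level, 80% power, 52 per group, raised to 57 per group for 10% loss. Section 8.3 gives the margin as .5. That discrepancy needs its own resolution; the figures here use 15, because the 52 rests on it.

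**Inputs not in the documents (assumptions).** Each physician's share of patients: one third. Difference in mean SPADI change for one physician's patients: 10 points. Share of the SD-20 variance lying between physicians, rho: 1% to 20%.

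**Step 1: reproduce the plan's figure.** n = 2 x SD² x (1.960 + 0.842)² / (15 - 4)² = 2 x 400 x 7.85 / 121 = 51.9, so 52 per group, as stated. Power at 52 is Phi(11 / (20 x sqrt(2/52)) - 1.960) = Phi(2.804 - 1.960) = 0.80. Allowing for loss gives 52 / 0.9 = 57.8 or 52 x 1.1 = 57.2; the stated 57 is close to either.

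**Step 2: chance imbalance.** For one given physician with share p = 1/3 and two given arms of 57, the between-arm difference in share has SD = sqrt(2 x p x (1 - p) / 57) = sqrt(2 x 0.3333 x 0.6667 / 57) = 0.088, or 8.8 percentage points. The 95% range is about ±17 points. The chance of a gap of at least 15 points is P(|Z| >= 0.15 / 0.0883 = 1.70), about 9%; of at least 20 points, P(|Z| >= 2.26), about 2%.

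**Step 3: effect on the comparison.** With the assumed 10-point difference, the shift is 0.15 x 10 = 1.5 to 0.20 x 10 = 2.0 points. That is 10% to 13% of the 15-point margin, and about half of one standard error (20 x sqrt(2/57) = 3.7).

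**Step 4: precision recoverable.** If SD 20 is the total SD, a physician term reduces the residual SD to 20 x sqrt(1 - rho). Power at 52 per arm is then Phi(11 / (20 x sqrt(1 - rho) x sqrt(2/52)) - 1.960). The true level when randomisation is stratified but the test is unadjusted is Phi(-1.960 / sqrt(1 - rho)).

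| rho (assumed) | Power, unadjusted | Power with physician term | n per arm with term | True level if stratified but unadjusted |
|---|---|---|---|---|
| 1% | 0.80 | 0.80 | 52 | 2.4% |
| 5% | 0.80 | 0.82 | 50 | 2.2% |
| 10% | 0.80 | 0.84 | 47 | 1.9% |
| 20% | 0.80 | 0.88 | 42 | 1.4% |

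The 10-point assumption of step 3 corresponds to 10² x (1/3) x (2/3) / 400 = 5.6% of the variance, so its row is close to 5%. If SD 20 is instead the within-physician SD (the plan does not say), unadjusted power is 0.80, 0.78, 0.76 and 0.71 at the four values of rho.

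**Step 5: does ignoring physician distort the test?** In simulation (20,000 trials per setting, 52 per arm, simple randomisation, caseloads equal or 60/25/15, rho from 0 to 20%), the unadjusted one-sided type I error was 0.024 to 0.028 against a nominal 0.025, and power was 0.79 to 0.80. With the physician term, power was 0.80 to 0.81 at rho 5%, 0.82 to 0.83 at 10% and 0.87 at 20%. At rho = 0 the term cost about 0.7 points of power (0.793 to 0.786 with equal caseloads).

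**The case against.** The strongest reply is that individual randomisation already deals with this. Every physician's patients can fall in any arm, and the unadjusted standard error already contains the between-physician variation. That is correct, and step 5 bears it out. A reader might infer that leaving physician out biases the dose comparison or inflates type I error; the design does not support that.

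The caseloads may also be similar. Eligibility criteria are common, a musculoskeletal radiologist grades the radiographs (7.2.1), there is one centre, and analysing change from baseline may remove part of any starting difference. These points make a small rho plausible but do not establish it.

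Other stronger readings fail too:
- One might suppose that the injecting physician decides which patients are referred. Sections 4.1 and 7.2.1 say otherwise: patients arrive by referral, already evaluated by the referring physician. No section says that the injectors differ in later care or surgical referral.
- One might quote a much higher imbalance frequency. A 15-point gap for some physician between some pair of arms occurs in about 42% of simulated trials, but that is the largest of nine differences. The shift in step 3 needs one particular physician and one particular pair, for which the figure is about 9%.
- One might argue that arms will often fall short of 52. This presumes unrestricted randomisation, which the protocol does not state, and it is separate from physician.

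**Conclusion.** The point holds as an inexpensive improvement in precision and balance, not as a flaw that threatens the conclusions. Physician is absent from the described randomisation and from the planned tests, and the reasons given in 7.2.2 do not cover differences between caseloads.

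The size is modest. A noticeable imbalance for a given physician and pair of arms is uncommon, and under the assumed 10-point difference the resulting shift is small against the 15-point margin. The gain in non-inferiority power runs from nothing at 1% of variance to about 8 points at 20%. The between-physician variance, the physician shares and the 10-point difference are all assumptions; the documents give none of them. No larger sample is needed if the SD of 20 is the total SD.

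**What to change.** In 7.2.2, state that patients are randomised 1:1:1 in permuted blocks of varying size, stratified by injecting physician (three strata).

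In 8.3, replace the two-sample tests with a linear model of SPADI change that includes physician as a factor, and take the 20 mg against 80 mg comparison and both non-inferiority comparisons from it. Adopt the two changes together, since stratifying without adjusting makes the tests conservative (last column of the table).

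Add a descriptive table of SPADI change by physician and arm, so that the expectation of minimal operator effect can be examined.

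The cost is three lists instead of one, some incomplete blocks when recruitment ends, two degrees of freedom, and under one point of power if physicians do not differ at all.

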7.2.3 Post-Clinic appointment

Patients will be contacted via telephone at 2 weeks to determine if any significant adverse outcomes have occurred. Patients will be contacted at 2 months, 4 months, and 6 months following the injection by email and/or phone call for completion of the SPADI and assessment of any adverse events that may have occurred as a result of the injection. Patients will also be asked what, if any, pain medications have been used in the month prior to the phone call. Patients will be given the option to complete the SPADI using the REDCap system or on paper. Patients wishing to complete the survey online will be emailed a link to access REDCap. A paper version of the survey will be mailed to the patient if that is their preferred method. A self-addressed stamped envelope will be included with the mailings. If the patient perceives that they have experienced an adverse effect the research coordinator will make a detailed record of the patient experience and the PI of the study will be contacted. .

At 12 months following the initial injection, in addition to a chart review, the patient will be contacted to determine the outcome of their shoulder pain and determine if the patient underwent any additional procedures and/or surgeries to the shoulder.

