1.0 Objectives

1.1 Study Objectives

The purpose of this study is to determine the most effective intraarticular steroid dose for the treatment of glenohumeral osteoarthritis. We aim to randomize patients into low, medium, and high dose groups of injectable corticosteroids as these doses are typically used in the standard of care for our patients. To date there has been no study to evaluate which dose is most efficient with the fewest side effects for glenohumeral osteoarthritis. Our objectives will be to provide ultrasound guided intraarticular glenohumeral injections of these randomized concentrations and to evaluate pain and function before and following injection with the Shoulder Pain and Disability Index (SPADI). We hypothesize that the low dose steroid will provide equivalent improvement of the pain and function to the medium and high doses, while minimizing side effects.

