2.0 Background

2.1 Scientific Background and Gaps

Osteoarthritis (OA) affects 54.4 million US adults and 23.7 million (43.5%) have arthritis-attributable activity limitation¹. As the condition progresses, pain and functional disability increase. Patients usually begin treatment with conservative measures including physical therapy and administration of nonsteroidal anti-inflammatory drugs before obtaining a corticosteroid injection². Corticosteroid injections have a patient-specific duration that often provide relief for a month before the effects begin to taper with most individuals returning to baseline by 2-3 months post injection^{3,4}.

Unfortunately, data on intraarticular injections is not robust and primarily focused on hip, knee, and disease processes rather than the glenohumeral joint⁶⁻⁸. For example, steroid concentrations have been studied in adhesive capsulitis, where 20 and 40mg of triamcinolone acetonide were used with no statistical significance between the two⁶. When a placebo was added, both doses were better than the placebo, but once again no difference was seen between the two steroid concentrations⁷. Another study, looking at knee osteoarthritis, found that high dose steroids had a larger effect on duration⁸, but other studies have shown no difference in duration between the 40mg and 80mg concentration of triamcinolone acetonide⁹.

Intraarticular injections do have adverse effects. Similar to steroids taken orally or intravenously, intraarticular injections have a similar side effect profile. Fortunately, intraarticular injections are localized, by the nature of the procedure, and the chances of experiencing a significant side effect is rare^{10,11}. The most common side effects are steroid flare, allergic reaction, facial erythema, hypo- pigmentation, fat pad necrosis, cutaneous atrophy, and a transient increase in blood glucose¹¹. Some of the rare side effects have been seen in case reports include idiopathic central serous chorioretinopathy, decrease in breast milk production, sepsis, tendon rupture, and cataracts¹¹. In addition, the administration of steroid injections are limited to being done every three months due to risk of weakening tendons, and acceleration of cartilage loss^{11,12}.

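### The first post-injection SPADI is at 2 months, inside the taper the protocol describes, so similar scores across doses, especially at 4 and 6 months, may reflect a worn-off effect.

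*Combined protocol and SAP*

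**What the plan says.** Section 1.2 sets the efficacy endpoint as "Change in Overall SPADI scores at baseline compared to 2,4, and 6 months". A baseline SPADI is taken at the clinic appointment (section 7.2.2): "After obtaining informed consent, the patient will be asked to complete the SPADI". Section 7.2.3 gives the later schedule: "Patients will be contacted at 2 months, 4 months, and 6 months following the injection by email and/or phone call for completion of the SPADI". An earlier contact with every patient exists in the same section, but its stated purpose is safety: "Patients will be contacted via telephone at 2 weeks to determine if any significant adverse outcomes have occurred".

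The only other early efficacy information is in section 7.2.2: "Pre and post pain levels will be elicited from patient". This is a pain level around the procedure. It is not the SPADI, it is not listed as an endpoint, and the injectate contains lidocaine.

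On duration of effect, section 2.1 says that injections "often provide relief for a month before the effects begin to taper with most individuals returning to baseline by 2-3 months post injection". The hypothesis in section 1.1 is one of similarity: "We hypothesize that the low dose steroid will provide equivalent improvement of the pain and function to the medium and high doses". Section 8.2 confirms that all arms are active: "This is a three arm trial comparing three different doses of steroid (20mg, 40mg, 80mg) in patients with glenohumeral arthritis". Sections 8.2 and 8.3 plan a two-sided t-test of 20 mg against 80 mg, and non-inferiority tests of 20 mg against 40 mg and of 40 mg against 80 mg.

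**The concern.** On the protocol's own description, no SPADI is taken in the month when relief is expected. The first measurement comes at the start of the period in which most patients are said to be back at baseline, and the other two come after it. No section justifies 2 months as the first efficacy time.

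This matters because of the kind of claim the trial wants to make. A non-inferiority conclusion is informative only if the treatments are doing something at the time of measurement. With no placebo arm, nothing in the design shows whether any dose is still working at a given visit. Waning relief then moves the data towards the trial's hypothesis and, for the same reason, removes the difference that the 20 mg against 80 mg test is meant to detect. The sample size in section 8.2 also assumes mean changes of 40, 36 and 32 points. Those are hard to square with most patients being near baseline for much of the 2- to 6-month period.

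**Working it through.** **Inputs from section 8.2.** Non-inferiority: SD 20, margin 15, true adjacent-dose difference 4, level 2.5% (taken as one-sided), power 80%, 52 per group. Superiority, 20 mg against 80 mg: effect size 0.5, two-sided 5%, 51 per group.

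**Step 1: reproduce the planned size.** n = 2 × [20 × (1.960 + 0.842) / (15 − 4)]² = 51.9, so 52 per group, as stated. This takes the 4-point difference as running against the dose under test.

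**Step 2: non-inferiority when part of the difference has gone.** Let f be the share of the peak between-dose difference still present at the visit. The documents give no value for f, so it is an assumption and is run over its whole range.

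SE = 20 × √(2/52) = 3.92

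P(declare non-inferior) = Φ[(15 − f × peak difference)/3.92 − 1.96]

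Example, peak difference 15 and f = 0.5: (15 − 7.5)/3.92 − 1.96 = −0.05, giving 48%.

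| Peak difference | f = 1 | 0.75 | 0.5 | 0.25 | 0 |
|---|---|---|---|---|---|
| 4 (the plan's value) | 80% | 86% | 91% | 95% | 97% |
| 15 (equal to the margin) | 2.5% | 16% | 48% | 82% | 97% |
| 20 (assumed) | 0.1% | 2.5% | 25% | 72% | 97% |

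At f = 0 the three rows agree, because the test no longer carries any information about the peak difference.

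**Step 3: the 20 mg against 80 mg test.** With a peak effect size of 0.5, 51 per group and a two-sided 5% t-test, power is 71%, 47%, 24%, 10% and 5% for the same values of f. (The starting value is 71% rather than 80% because 51 per group matches a one-sided calculation; that is a separate point.)

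**Step 4: dependence on the margin.** Section 8.3 gives the margin as .5, not 15. If that means half an SD, it is 0.5 × 20 = 10 points. Replacing 15 by 10 as the margin in the formula, a dose 15 points worse at peak passes about 0.1%, 1%, 9%, 36% and 72% of the time. The direction is the same and the figures are smaller. The two sections must be reconciled before any one set of percentages is relied on.

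**The case against.** The strongest reply has four parts.

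- **2 months is not too late by the protocol's account.** Section 2.1 has the effect starting to taper after a month, with most patients back at baseline by 2 to 3 months. Some effect may remain at 2 months. If half does, a dose 20 points worse at peak would still fail non-inferiority about 75% of the time (100% − 25%). This stands. A reader might infer that non-inferiority would be reached whatever the doses did, or that the trial cannot say which dose is most effective. The documents do not support that: it describes f = 0, which fits 4 and 6 months at most.
- **The duration statement is soft.** It is qualified as patient-specific and as applying often or to most people, and the two sources cited for it are knee reviews by title. Whether it carries over to the shoulder is unknown. This stands, and is why the size is given as a range. It remains the only statement of duration in the protocol.
- **Dose may act on duration.** Section 2.1 mentions a knee study in which high dose lasted longer, alongside others that found no difference, and section 12.2 names duration as an aim. The arms might then be alike early and differ later, and a 2-week SPADI alone could mislead in the other direction. This stands. It argues for keeping the later visits, not against adding an early one.
- **Late visits have a purpose.** Section 2.1 says injections are limited to every three months, so benefit towards the end of that interval is a fair question. This also stands. It does not explain the absence of any earlier SPADI.

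It is also fair to say that each test remains valid for the difference at its own visit. The problem is what a similar result can be taken to mean.

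**Conclusion.** The concern holds in a limited form. The schedule has no post-injection SPADI in the period when section 2.1 expects most relief, and the protocol neither justifies this nor says how similarity at a late visit will be told apart from a worn-off effect. Similarity at 4 and 6 months is the most exposed; at 2 months the exposure is partial.

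The size cannot be fixed from the documents. On the section 8.2 inputs, the chance of passing a dose that was worse by the full margin at peak runs from the nominal 2.5% to 97% as the remaining share falls from all to none. That rests on three assumptions: that the between-dose difference is largest early and then shrinks, that SD 20 applies at the visit, and that the margin is 15. Section 2.1 describes relief within patients, not the contrast between doses, so the first of these is not documented. The planned analyses can still be run. This is a cheap improvement worth making before enrolment proceeds, because an early measurement cannot be recovered afterwards.

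**What to change.** - In section 7.2.3, add the SPADI to the existing 2-week contact, completed by the REDCap or paper routes already provided. Keep the 2-, 4- and 6-month visits unchanged.
- In section 8.3, pre-specify the 20 mg against 80 mg comparison and the two non-inferiority comparisons at 2 weeks as secondary analyses, outside the primary error control.
- State that non-inferiority at 2, 4 or 6 months will be interpreted alongside the 2-week result and the mean change from baseline in each arm at that visit.
- Reconcile the margin of 15 in section 8.2 with the .5 in section 8.3, so that the same margin applies at every time point.

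The cost is one more short questionnaire per patient, some mailing for those who choose paper, one more secondary time point to report, and the wording changes. No extra visit, larger sample or change of treatment is needed.
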